### 2 Introduction

### 2.1 Preface

Blood Pressure is a multi-regulated variable depending on many compensating pathways. Consequently, combinations of drugs, working through different mechanisms, are required to reduce BP in most people with hypertension. Thus, monotherapy is likely to be inadequate therapy in most patients. Indeed, almost all patients in RCTs have required combinations of drugs to control their BP.

Zofenopril (ZOF) has been widely investigated for the treatment of patients with hypertension and its BP lowering effect has been compared with either placebo or with all the classes of antihypertensive drugs currently recommended for the treatment of hypertension. Although there are data in literature showing an added antihypertensive effect of Amlodipine (AML) or Zofenopril to other antihypertensive treatment, there is scarce evidence at the moment on the antihypertensive effect of the extemporaneous combination of ZOF and AML versus each monotherapy. The trial will be conducted in compliance with the protocol, GCP and the applicable regulatory requirements.

### 2.2 Purpose of the Analysis

These analyses will assess the anti-hypertensive efficacy and safety of the extemporaneous combination of ZOF 30 mg with AML 5 mg or AML 10 mg. Results will be included in the Clinical Study Report (CSR).

### 3 Study Objectives and Endpoints

### 3.1 Study Objectives

### 3.1.1 Primary Objectives

• **Objective 1.1**: To assess the anti-hypertensive efficacy of the extemporaneous combination of ZOF 30 mg with AML 5 mg or AML 10 mg in lowering the sitting diastolic BP between Visit 2 (Week 0) and Visit 4 (Week 8) in patients with uncontrolled BP previously treated with Zofenopril or Amlodipine (5 mg) monotherapies for at least 4 weeks.

#### 3.1.2 Secondary Objectives

- **Objective 2.1**: To assess the antihypertensive efficacy of the extemporaneous combination of ZOF 30 mg in combination with AML 5 mg or AML 10 mg in lowering sitting systolic BP (SBP) between Visit 2 (Week 0) and Visit 4 (Week 8) in patients with uncontrolled BP previously treated with ZOF or AML 5 mg monotherapies for at least 4 weeks.
- **Objective 2.2**: To assess the antihypertensive efficacy of the extemporaneous combination of ZOF/AML 30/10 mg vs. ZOF/AML 30/5 mg, in lowering sitting DBP and SBP between Visit 3 (Week 4) and Visit 4 (Week 8) in patients with uncontrolled BP previously treated with ZOF or AML 5 mg monotherapies for at least 4 weeks.
- **Objective 2.3**: Monotherapy: to evaluate the total number and percentage of patients who achieved the BP goal (sitting BP ≤130/80 mmHg) at Visit 2 (Week 0). Combination therapy: to

evaluate the total number and percentage of patients who achieved the BP goal (sitting BP  $\leq$ 130/80 mmHg) at Visit 3 (Week 4) and Visit 4 (week 8).

- **Objective 2.4**: To assess the compliance to the treatment (percentage of actual doses taken versus doses to be taken) at Visit 2 (Week 0), at Visit 3 (Week 4) and at Visit 4 (Week 8).
- **Objective 2.5**: To evaluate the safety and tolerability of the monotherapies (ZOF 30 mg and AML 5 mg) after 4 weeks of therapy and of the extemporaneous combinations (ZOF 30 mg and AML 5 mg or AML 10 mg) after 8 weeks of treatment.

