- b. Only patients controlled at Visit 3 will receive ZOF/AML 30/5 mg
- c. Only patients uncontrolled at Visit 3 will receive ZOF/AML 30/10 mg.
- d. To ensure patient safety, the patients will be contacted over phone within 24 hours, in case of any abnormality and clinically relevant laboratory test according to the Investigator's judgement at any visit
- e. The Investigator is expected to also record any AE which was ongoing at the last treatment dose and a follow-up phone call should be made after 2 weeks from the last study visit.

In case AE was ongoing, the Investigator is expected to follow-up until the outcome of the AE has been determined.

- f. IWRS- Interactive Web Response System
- g. The following procedure is applied only in case of COVID-19 restrictions.
- h. Patients will be provided with an automatic blood pressure device to be used in case they are not able to go to the study centre due to Covid-19 pandemic situation.
- i. The patient will return the device at the last visit at the site

MENARINI	Согр	porate Medical Departmo	ent
Identification Number	Version Number	State	Effective date
FORM-000050125	2.0, CURRENT	Effective	08, Jan 2021

Protocol Version 1.0 of 1 23/04/2021

Study Code: MEIN/20/ZoAm-Hyp/001

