After 4 weeks  $\pm$  2 days from Visit 2, during the assessment period patients receiving the extemporaneous combination of ZOF 30 mg and AML 5 mg, will be further evaluated (Visit 3): controlled patients (sitting SBP/DBP  $\leq$ 130/80 mmHg) will continue the same extemporaneous combination for additional 4 weeks  $\pm$  2 days, while uncontrolled patients (sitting SBP/DBP >130/80 mmHg) will be up-titrated from ZOF/AML 30/5 mg to ZOF/AML 30/10 mg for further 4 weeks  $\pm$  2 days.

At Visit 3 patients with SBP/DBP values classified as Grade 3 (SBP  $\geq$  180 or DBP  $\geq$  110 mmHg) hypertension will be withdrawn from the study.

If patients at Visit 3, do not tolerate the extemporaneous combination treatment or they have an adherence range below 80% or superior to 120%, they will be withdrawn from the study. At the end of the assessment period (8 weeks  $\pm$  4 days) at Visit 4, the anti-hypertensive effect of the extemporaneous combination (ZOF/AML 30/5 mg and ZOF/AML 30/10 mg) will be evaluated.

Efforts will be made to achieve 1:1 ratio in the enrolment of patients receiving any ACE-i or allowed CCBs. At Visit 2, a minimum of 45% of uncontrolled patients receiving treatment with ZOF 30 mg or AML 5 mg are required to enter the assessment period, in order to maintain a balance between the 2 treatments during the assessment period.

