### 7.1 Efficacy Variable Derivations

### 7.1.1 Blood Pressure (BP) Goal (Controlled v Uncontrolled)

Multiple endpoints (2.3, 3.3, and 3.4) involve patients meeting the BP goal of sitting  $BP \le 130/80$  mmHg at Visit 2 (Week 0), Visit 3 (Week 4) and Visit 4 (Week 8).

A patient will be considered to have met the BP goal (controlled BP) if their SBP  $\leq$  130 mmHg AND their DBP  $\leq$  80 mmHg. If a patient meets one of these criteria but not the other, then they will not be considered to have met the BP goal. That is, a patient's BP is considered uncontrolled if their SBP > 130 mmHg OR their DBP > 80 mmHg.

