#### 7.3.1 Mean Change (Endpoints 2.1 and 2.2)

Endpoint 2.1: Change in mean sitting SBP between Visit 2 (Week 0) and Visit 4 (Week 8).

Endpoint 2.1 will be analyzed using a paired t-test with a type I error rate of 0.05 to test the null hypothesis that the mean change in SBP is 0 mmHg from Visit 2 to Visit 4 against a two-sided alternative.

**Endpoint 2.2**: Change in mean sitting DBP and SBP between Visit 3 (Week 4) and Visit 4 (Week 8) in patients uncontrolled at Visit 3 and up titrated to the extemporaneous combination of ZOF/AML 30/10 mg.

Endpoint 2.2 will be analyzed using paired t-test for DBP and SBP with a type I error rate of 0.05 to test the null hypotheses of 0 mmHg mean change from Visit 3 to Visit 4 against a two-sided alternative.

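### Objective 2.2 states a 30/10 mg versus 30/5 mg comparison, but Endpoint 2.2 is an uncontrolled change from the same Visit 3 reading that selects patients for up-titration, so it cannot support a dose conclusion

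*SAP*

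**What the plan says.** The objective, worded alike in the protocol (synopsis and section 4) and SAP 3.1.2, concerns the "extemporaneous combination of ZOF/AML 30/10 mg vs. ZOF/AML 30/5 mg" for sitting DBP and SBP between Visit 3 and Visit 4.

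The analysis (SAP 7.3.1; protocol 12.5.4) is of the change "in patients uncontrolled at Visit 3 and up titrated". It uses paired t-tests, for DBP and SBP, to "test the null hypotheses of 0 mmHg mean change from Visit 3 to Visit 4 against a two-sided alternative".

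Dose after Visit 3 is fixed by the Visit 3 reading:

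- SAP 7.1.1: "a patient's BP is considered uncontrolled if their SBP > 130 mmHg" or DBP is above 80 mmHg.
- Protocol 2.2, flow chart footnotes: "Only patients uncontrolled at Visit 3 will receive ZOF/AML 30/10 mg", and "Only patients controlled at Visit 3 will receive ZOF/AML 30/5 mg".
- SAP 4.1: patients at Visit 3 whose values are classed as Grade 3 "hypertension will be withdrawn from the study".

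The study is non-randomised and unblinded (SAP 4.5). Inferential tables use only the All Patients column unless otherwise specified (SAP 5.5), and the shell for Endpoint 2.2 (Table 14.2.3.2) has no 30/5 column. The by-dose blood pressure tables (14.2.1.1 to 14.2.1.4) are descriptive. The listed sensitivity analyses concern Endpoint 1.1 only (SAP 7.2.2), secondary endpoints are not adjusted for multiplicity (SAP 5.9), and neither document mentions regression to the mean.

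**The concern.** The stated question is whether 30/10 lowers pressure more than 30/5. The planned test asks whether pressure changed in patients picked because it was high at the start of the interval. Such patients are expected to read lower next time whether or not the dose change does anything. A significant fall in DBP and SBP could then be reported under an objective that names 30/5 as the comparator, although the design has no patient who is uncontrolled at Visit 3 and stays on 30/5. At stake is whether the report can say anything about the added efficacy of the higher dose.

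**Working it through.** **Plan's own figure.** There is no size or power for Endpoint 2.2. The only calculation is for the primary endpoint: 216 patients, mean 4 against a null of 2 mmHg, SD 10. It reproduces with a one-sided 5% test: (10 × (1.645 + 1.282) / 2)² = 214.2, so 215 by the normal formula and 216 by the t distribution (power 90.07%). It is used here only for N = 216 and for an upper limit on visit-to-visit DBP variation: 10/√2 = 7.07. That SD is for Visit 2 to Visit 4, so it is a guide and not a value for Visit 3 to Visit 4.

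**Assumed, not in the documents.** Visit 3 means 130/80 to 140/88; between-patient SD 12 (SBP) and 8 (DBP); visit-to-visit DBP SD 4 to 7.07, SBP SD 1.6 times that; SBP/DBP correlation 0.6; no effect of up-titration and no time trend.

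**Step 1, the bias.** Write each reading as a patient's own level (SD s_b) plus visit variation (SD s_w). With no treatment effect, the expected Visit 3 to Visit 4 change in the selected group is close to

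−[s_w² / (s_b² + s_w²)] × (mean Visit 3 in the selected − mean Visit 3 in all).

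The bracket is positive if there is any visit-to-visit variation, and the selected group lies above the overall mean, so the result is a fall. Averaging three readings at one visit (protocol 8.1) does not remove variation between visits.

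Example, means 135/84 and DBP s_w = 5.5: 30.25 / (64 + 30.25) = 0.321. The selected lie about 3.1 mmHg above the overall mean, so the fall is 0.321 × 3.1 ≈ 1.0 mmHg. Simulation also gives about 1.0.

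**Step 2, chance of p ≤ 0.05 (nominal 5%), by simulation.**

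| Visit 3 mean, DBP s_w | Up-titrated of 216 | Spurious DBP fall | p ≤ 0.05 |
|---|---|---|---|
| 130/80, 7.07 | 139 | 2.3 | 80% |
| 140/88, 4 | 192 | 0.3 | 11% |

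Hand check, first row: the SD of change is about 9.5 (selection trims it from 10), SE = 9.5/√139 = 0.81, 2.3/0.81 = 2.8, and Φ(2.8 − 1.98) ≈ 0.8. Second row: SD = 4√2 = 5.66, SE = 5.66/√192 = 0.41, 0.3/0.41 = 0.73, and Φ(0.73 − 1.97) ≈ 0.11. The SBP falls across these scenarios are 0.5 to 3.7 mmHg.

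**Step 3, with the entry rules applied.** Patients enter at SBP ≥140 and/or DBP ≥90 and must still be uncontrolled at Visit 2. Assume population means of 138/86 or 145/90 and a true fall of 5/4 mmHg by Visit 3. Visit 3 means are then about 139–144/85–88, 86% to 97% are up-titrated, the spurious DBP fall is 0.1 to 1.1 mmHg and rejection is 6% to 34%. A larger true fall of 10/7 gives rejection of 15% to about 70%.

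**Step 4, other variances.** With between-patient SD 9/6 and no entry rules (significant DBP falls only, nominal 2.5%):

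| Visit 3 mean | Spurious DBP fall | Significant fall |
|---|---|---|
| 128/78 | 1.3–3.1 | 76–95% |
| 130/80 | 1.1–2.7 | 66–91% |
| 136/84 | 0.6–1.6 | 28–60% |
| 142/88 | 0.2–0.8 | 10–19% |

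The pattern is the same and the level moves with the inputs.

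**Step 5, the patients left on 30/5.** They are selected for low Visit 3 readings and drift upward with no treatment change: 1.6 to 6.8 mmHg DBP under the Step 2 assumptions. Setting the two groups against each other would therefore add a second bias in favour of 30/10.

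**The case against.** The best defence is that the comparison was always meant within patients. Every up-titrated patient is on 30/5 up to Visit 3 and on 30/10 up to Visit 4, the objective names those two visits, and the endpoint paired with it in protocol section 4 describes exactly that group. Population and test agree between protocol and SAP. This reading is fair, and a reader who infers that a between-group analysis was promised and then dropped goes further than the documents allow. But the within-patient reading is the one exposed to regression and time effects, so it explains the wording without rescuing the inference.

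Two other strong readings also fail. A reader might infer that the plan will declare 30/10 superior. It sets an explicit decision rule only for the primary endpoint (SAP 7.2.1), secondary endpoints are to support that conclusion (SAP 5.9), and Table 14.2.3.2 shows the mean change and CI beside the p-value. A reader might also say the t-test has no valid error rate. For its stated null, "null hypotheses of 0 mmHg mean change from Visit 3 to Visit 4", it is an ordinary test; what fails is attributing a rejection to the dose.

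The objection that the size is assumption-driven stands. The highest rates need Visit 3 means near or below 130/80, and the entry criteria together with the 4 mmHg DBP fall assumed for the primary endpoint suggest that they may be higher.

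**Conclusion.** The mismatch is established from the text: the objective names 30/5 as comparator, and the only test is an uncontrolled change in patients selected on its own baseline. The regression component is a fall whenever pressure varies between visits; four more weeks of treatment is a further unseparated contribution.

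The size is not established. With between-patient SD 12/8 and no up-titration effect, the spurious DBP fall is about 0.1 to 2.3 mmHg and the chance of p ≤ 0.05 about 6% to 80%. Narrower between-patient spread and Visit 3 means below goal raise the upper end, to 3.1 mmHg and 95%. The bias is slight if nearly all patients are up-titrated, which cannot be known in advance.

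It would be tempting to keep a formal test and replace 0 by the expected regression, using the slope b of Visit 2 on Visit 1 pressure to estimate it. That is not sound here. With the entry rules applied, this under-corrects by roughly 20% to 50%: a true DBP fall of 1.11 is estimated as 0.73 (1 − 0.73/1.11 = 34% short), and an SBP fall of 0.97 as 0.50 (48% short). It also treats b as known. The number continuing the same monotherapy is not stated; if it were 60, the standard error of b would be about 0.10 to 0.16.

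**What to change.** 1. Reword Objective 2.2 in the protocol (synopsis and section 4) and SAP 3.1.2 as: *change in DBP and SBP from Visit 3 to Visit 4 after up-titration in patients uncontrolled on ZOF/AML 30/5*. Delete the comparison with 30/5.
2. In SAP 7.3.1 and Table 14.2.3.2, report the mean change with its 95% CI as descriptive. State that the Visit 3 reading both selects patients and serves as baseline, so part of any fall may be regression to the mean or further time on treatment.
3. State that no 30/10 versus 30/5 conclusion will be drawn from the p-value, or from setting up-titrated patients against those left on 30/5.
4. Keep 0 as the reference if a test is shown. A regression-adjusted estimate may be added only as a sensitivity analysis that allows for entry selection and for the uncertainty in the slope, for example by bootstrap.

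The cost is a wording change in both documents and a table footnote. No new data are needed, and the primary endpoint and patient management are untouched. The price is that the trial gives up a claim of added efficacy of 30/10 over 30/5.

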### 3.1.3 Exploratory Objectives

- **Objective 3.1**: To assess change in mean sitting SBP and DBP between Visit 1 (Week -4) and Visit 2 (Week 0), Visit 3 (Week 4) and Visit 4 (Week 8).
- **Objective 3.2**: To assess the antihypertensive efficacy at different time points in patients who (1) received ZOF or AML monotherapies before the run-in period, (2) received any other ACE-i or CCB monotherapies before the run-in period.

### 3.2 Endpoints

### 3.2.1 Primary Endpoints

• Endpoint 1.1: Change in mean sitting DBP between Visit 2 (Week 0) and Visit 4 (Week 8).

#### 3.2.2 Secondary Endpoints

- Endpoint 2.1: Change in mean sitting SBP between Visit 2 (Week 0) and Visit 4 (Week 8).
- Endpoint 2.2: Change in mean sitting DBP and SBP between Visit 3 (Week 4) and 4 (Week 8) in patients on combination of ZOF/AML 30/5 with uncontrolled BP at Visit 3 and up titrated to the extemporaneous combination of ZOF/AML 30/10 mg.
- Endpoint 2.3: Monotherapy: number and proportion of patients achieving the BP goal (sitting BP≤130/80 mmHg) at Visit 2 (Week 0). Combination therapy: number and proportion of patients achieving the BP goal (sitting BP≤130/80 mmHg) at Visit 3 (Week 4) and Visit 4 (Week 8).
- Endpoint 2.4: Adherence to the treatments (percentage (%) of doses taken/ doses to be taken) at Visit 2 (Week 0), Visit 3 (Week 4) and Visit 4 (Week 8).
- Endpoint 2.5: Safety and tolerability of the monotherapies (ZOF 30 mg and AML 5 mg) after 4 weeks of therapy and of the extemporaneous combination (ZOF 30 mg and AML 5 mg or AML 10 mg) after eight weeks of treatment.

### 3.2.3 Exploratory Endpoints

- Endpoint 3.1: Change in mean sitting SBP and DBP between Visit 1 (week -4) and Visit 2 (Week 0), visit 3 (Week 4) and Visit 4 (Week 8):
  - In the group of patients who were on ZOF 30 mg and AML 5 mg at Visit 1 (Week -4) and continued the same therapies.

- In the group of patients who switched to ZOF 30 mg or AML 5 mg from any other ACE-i or CCBs at Visit 1 (Week -4).
- Endpoint 3.2: Change in mean sitting SBP and DBP for uncontrolled patients at Visit 3 (Week 4), between Visit 2 (Week 0) and Visit 3 (Week 4).
  - In the group of patients who were on ZOF 30 mg and AML 5 mg at Visit 1 (Week -4) and continued the same therapies.
  - In the group of patients who switched to ZOF 30 mg or AML 5 mg from any other ACE-i or CCBs at Visit 1 (Week -4).
- Endpoint 3.3:
  - Monotherapy: number and proportion of patients achieving the BP goal (sitting BP≤130/80 mmHg) at Visit 2 (Week 0):
    - In the group of patients who were on ZOF 30 mg and AML 5 mg at Visit 1 (Week -4) and continued the same therapies.
    - In the group of patients who switched to ZOF 30 mg or AML 5 mg from any other ACE-i or CCBs at Visit 1 (Week -4).
  - Combination therapy: number and proportion of patients achieving the BP goal (sitting BP≤130/80 mmHg) at Visit 3 (Week 4):
    - In the group of patients who were on ZOF 30 mg and AML 5 mg at Visit 1 (Week -4) and continued the same therapies.
    - In the group of patients who switched to ZOF 30 mg or AML 5 mg from any other ACE-i or CCBs at Visit 1 (Week -4).

### • Endpoint 3.4:

- Monotherapy: number and proportion of patients divided in subgroup by the hypertension grade, the presence of diabetes and/or of hypercholesterolemia achieving the BP goal (sitting BP ≤130/80 mmHg) at Visit 2 (Week 0):
  - In the group of patients who were on ZOF 30 mg and AML 5 mg at Visit 1 (Week -4) and continued the same therapies.
  - In the group of patients who switched to ZOF 30 mg or AML 5 mg from any other ACE-i or CCBs at Visit 1 (Week -4).
- Combination therapy: number and proportion of patients divided in subgroup by the hypertension grade, the presence of diabetes and/or of hypercholesterolemia achieving the BP goal (sitting BP ≤130/80 mmHg) at Visit 3 (Week 4) and Visit 4 (Week 8):
  - In the group of patients who were on ZOF 30 mg and AML 5 mg at Visit 1 (Week -4) and continued the same therapies.
  - In the group of patients who switched to ZOF 30 mg or AML 5 mg from any other ACE-i or CCBs at Visit 1 (Week -4).

### 4 Study Methods

### 4.1 General Study Design and Plan

This is a phase IV, open-label, multicenter, multinational study with 2 study periods: a 4-week run-in period and an 8-week assessment period.

Approximately 290 patients are planned to be screened to ensure at least 216 patients complete the run-in period and start with the assessment period.

Patients with Grade 1-2 hypertensive patients (blood pressure [BP] ranging from  $\geq$ 140/90 mmHg to  $\leq$ 179/109 mmHg) on treatment with any angiotensin converting enzyme inhibitors (ACE-i) including Zofenopril 30 mg or with calcium channel blockers (CCBs) including Amlodipine 5 mg will be screened for eligibility (Visit 1).

Allowed CCBs: Felodipine, isradipine, lacidipine, lercanidipine, nicardipine, nifedipine, and nisoldipine. Patients treated with other dosages of Zofenopril (other than 30 mg) are not allowed to be screened.

After screening, on the same day, eligible patients, will enter into a 4-week run-in period, during which patients on other ACE-i will be assigned to monotherapy with ZOF 30 mg while patients on CCBs will be assigned to monotherapy with AML 5 mg for 4 weeks. Patients with on-going treatment zofenopril 30 mg and amlodipine 5mg will continue on the same treatment for 4 weeks.

After the run-in period (4 weeks  $\pm$  2 days), BP will be further assessed (Visit 2), if BP levels are over the defined controlled target goal (sitting SBP/DBP >130/80 mmHg), treatment is well tolerated and adherence to the treatments ranges from 80% to 120%, patients will enter the assessment period, where they will be assigned to the extemporaneous combination of ZOF 30 mg and AML 5 mg. At Visit 2 patients with SBP/DBP values classified as Grade 3 (SBP  $\geq$  180 or DBP  $\geq$  110 mmHg) hypertension will be withdrawn from the study.

If patients, at Visit 2, after the run-in period, have a controlled BP (sitting SBP/DBP≤130/80 mmHg) or do not tolerate the treatment or have an adherence range below 80% or superior to 120%, they will be withdrawn from the study.

The patients will be assessed for further 8 weeks (assessment period).

After 4 weeks  $\pm$  2 days from Visit 2, during the assessment period patients receiving the extemporaneous combination of ZOF 30 mg and AML 5 mg, will be further evaluated (Visit 3): controlled patients (sitting SBP/DBP  $\leq$ 130/80 mmHg) will continue the same extemporaneous combination for additional 4 weeks  $\pm$  2 days, while uncontrolled patients (sitting SBP/DBP >130/80 mmHg) will be up-titrated from ZOF/AML 30/5 mg to ZOF/AML 30/10 mg for further 4 weeks  $\pm$  2 days.

At Visit 3 patients with SBP/DBP values classified as Grade 3 (SBP  $\geq$  180 or DBP  $\geq$  110 mmHg) hypertension will be withdrawn from the study.

If patients at Visit 3, do not tolerate the extemporaneous combination treatment or they have an adherence range below 80% or superior to 120%, they will be withdrawn from the study. At the end of the assessment period (8 weeks  $\pm$  4 days) at Visit 4, the anti-hypertensive effect of the extemporaneous combination (ZOF/AML 30/5 mg and ZOF/AML 30/10 mg) will be evaluated.

Efforts will be made to achieve 1:1 ratio in the enrolment of patients receiving any ACE-i or allowed CCBs. At Visit 2, a minimum of 45% of uncontrolled patients receiving treatment with ZOF 30 mg or AML 5 mg are required to enter the assessment period, in order to maintain a balance between the 2 treatments during the assessment period.

